2.2.3. Exploratory Endpoints

- 
-
-
-

3. STUDY DESIGN

3.1. Summary of Study Design

This is an open-label, single-arm, global Phase 2 study to evaluate the efficacy and safety of single-agent poly (ADP-ribose) polymerase 1 and 2 (PARP1/2) inhibitor pamiparib in mCRPC patients with CTC-HRD-positive disease or who have a deleterious germline or somatic mutation in BRCA1 or BRCA2.

To be eligible for the study, biomarker-positive patients must have progressed on or after at least one androgen receptor-targeted therapy for mCRPC (eg, enzalutamide, abiraterone acetate/prednisone, bicalutamide, flutamide, apalutamide, or nilutamide), received at least 1 taxane-based therapy for metastatic prostate cancer, and have PSA progression as per PCWG3 criteria at time of study entry. The primary endpoints are ORR by IRC for patients with measurable disease ($n \approx 50$) and PSA response rate for patients with or without measurable disease ($n \approx 80$) as per PCWG3 criteria.

Cohort 1 will include 50 mCRPC patients with CTC-HRD-positive, measurable metastatic disease (soft tissue with/without bone lesions), and positive BRCA1/2 mutation or negative/unknown BRCA1/2 mutation. Cohort 2 will include 30 mCRPC CTC-HRD positive patients with bone metastasis only and positive or negative/unknown BRCA1/2. Cohort 3 and 4 will include 20 mCRPC CTC-HRD negative/unknown patients with BRCA1/2 positive mutations, metastatic disease (measurable soft tissue with/without bone), and bone only (see [Table 2](#)).

After enrollment, patients will receive pamiparib 60 mg orally twice a day in cycles of 28 days.

Safety assessments will occur on Day 1 of each cycle, on Day 15 of Cycles 1 and 2, and as needed. Dose modifications will be made if appropriate ([Section 6.1.4](#)). AEs will be followed and documented during the treatment phase and for approximately 30 days after the last dose of pamiparib or until initiation of new anticancer therapy, whichever occurs first ([Section 9](#) and [Appendix 1](#)). AEs will be graded according to NCI-CTCAE Version 4.03 or higher. A Safety Monitoring Committee will periodically review safety data.

PK samples for pamiparib will be collected at various timepoints at all non-China centers and at centers with such capability in China. In addition, tumor tissue (if available) and blood samples will

be obtained to explore biomarkers of pharmacodynamics, response, and resistance to pamiparib in mCRPC.

[figure not shown]
Disease status will be assessed by the investigator using PCWG3 criteria ([Appendix 10](#)). Patients will undergo tumor assessments every 8 weeks (± 7 days) for 24 weeks, then every 12 weeks (± 7 days), or as clinically indicated. PSA assessments will occur at screening, on Day 1, and then every 4 weeks (± 7 days), or as clinically indicated.

Administration of pamiparib will continue until PD, unacceptable toxicity, death, or another discontinuation criterion is met ([Sections 5.5.1](#) and [5.6.4](#)). Once the treatment phase has been completed, an End-of-Treatment (EOT) Visit should occur within 7 days of stopping pamiparib with subsequent phases of safety and long-term follow-up.

Long-term follow-up will include tumor and PSA assessments every 12 weeks and 4 weeks (± 7 days), respectively, for those patients without PD, survival status, and initiation of new anticancer therapy. Long-term follow-up will continue until the patient dies or another criterion for discontinuation from study is met ([Section 5.6.4](#)).

Study procedures and assessments are detailed in [Section 7](#) and [Appendix 1](#). The patient cohorts are presented in [Table 2](#) and study schema is presented in [Figure 2](#).

Figure 2: Study Schema

Abbreviations: CTC-HRD+, positive for circulating tumor cells with homologous recombination deficiency per Epic Sciences assay; mCRPC, metastatic castration-resistant prostate cancer; PARPi, PARP inhibitor; PCWG3, Prostate Cancer Clinical Trials Working Group 3; PD, progressive disease; PSA, prostate-specific antigen; RECIST, Response Evaluation Criteria in Solid Tumors.

Notes: Key assessments during the treatment phase: tumor assessments every 8 weeks (\pm 7 days) for 24 weeks, then every 12 weeks (\pm 7 days), or as clinically indicated; and patient-reported outcomes, PSA, adverse events, hematology, and chemistry every 4 weeks. Pamiparib is to be administered continuously.

Table 2: Patient Cohorts

Cohort	1		2		3	4
Patients	n ≈ 50		n ≈ 30		n ≈ 20	
CTC-HRD	+		+		-/∅	
Metastatic disease	Measurable soft tissue ± bone		Bone only		Measurable soft tissue ± bone	Bone only
BRCA1/2 mutation	1A: +	1B: -/∅	2A: +	2B: -/∅	+	

Abbreviations: ∅, biomarker status unknown; CTC-HRD-, negative for circulating tumor cells with homologous recombination deficiency per Epic Sciences assay; CTC-HRD+, positive for circulating tumor cells with homologous recombination deficiency per Epic Sciences assay.

3.2. Safety Monitoring Committee

The Safety Monitoring Committee will be composed, at a minimum, of clinicians and a statistician. These members will have experience in the fields of oncology, clinical study conduct and monitoring, and biostatistics.

The Safety Monitoring Committee will provide safety oversight for the study population and will advise the study team of the need for study modification or termination based on regular reviews of accumulating safety data. Regular safety monitoring will be performed by the Safety Monitoring Committee. Details of the membership, scope of data review, and meeting frequency will be provided in the Safety Monitoring Committee charter.

Following Safety Monitoring Committee review and discussion, the sponsor will make final decisions regarding any change in the study conduct. Please see the details in the Safety Monitoring Committee charter.

3.3. Independent Review Committee

Tumor images will be collected and reviewed by the IRC for baseline tumor status during screening, on-study tumor monitoring, and adjudication of the selected efficacy endpoints. The protocol-specific review function and processes of the IRC will be described in the IRC charter.

3.4. Duration of the Study

The duration of the study from first enrolled patient to last patient is off study is estimated to be approximately 31 months.

4. STUDY POPULATION

4.1. Inclusion Criteria

Patients must meet all of the following criteria to be eligible for the study:

1. Sign informed consent form (ICF): must be able to provide written informed consent and can understand the nature, significance, and consequences of participating in the clinical study
2. Agrees not to participate in another interventional study while on pamiparib
3. If receiving bisphosphonate or other approved bone-targeting therapy, must have been on stable doses for at ≥ 28 days before start of pamiparib on Day 1
4. Adult males ≥ 18 years of age at the time of informed consent and has signed informed consent before any study-related activities and according to local guidelines
5. Histologically or cytologically confirmed adenocarcinoma or poorly differentiated adenocarcinoma of the prostate without neuroendocrine differentiation
 - Mixed histology is acceptable.
 - Pure small cell histology is excluded.

6. Metastatic castration-resistant prostate cancer (mCRPC) with 1 or 2 of the following:
 - a) Measurable disease as per Response Evaluation Criteria in Solid Tumors (RECIST) Version 1.1 ([Appendix 2](#)), involving viscera (lung, liver, adrenal glands, or other) and/or extrapelvic nodes (retroperitoneal, mediastinal, thoracic, or other)
 - b) Bone disease
7. Prostate cancer progression defined as follows:
 - a) Prostate-specific antigen (PSA) progression with ≥ 3 rising PSA levels with ≥ 1 week between determinations
 - b) Screening PSA ≥ 2 $\mu\text{g/L}$ (2 ng/mL)
8. Surgical or medical castration (bilateral orchiectomy or ongoing treatment with a gonadotropin-releasing hormone [GnRH] agonist or antagonist, respectively)
9. Serum testosterone ≤ 1.73 nmol/L (or ≤ 50 ng/dL) at screening
10. ≥ 1 androgen receptor-targeted therapy for mCRPC (eg, enzalutamide, abiraterone acetate/prednisone, bicalutamide, flutamide, apalutamide, or nilutamide)
11. ≥ 1 taxane-based therapy for metastatic castration-resistant prostate cancer
12. Prostate cancer with homologous recombination deficiency (HRD) as evidenced by 1 or 2 of the following:
 - a) Positive for circulating tumor cells with homologous recombination deficiency per Epic Sciences assay (CTC-HRD-positive)
 - b) Deleterious germline or somatic mutation in BRCA1 or BRCA2
13. Agreement to provide tumor tissue, if available, and blood samples for molecular analysis
 - Note: If archival tumor tissue is not available, an optional fresh biopsy is highly recommended.
14. Eastern Cooperative Oncology Group (ECOG) performance status ≤ 1 ([Appendix 3](#))
15. Ability to swallow whole capsules
16. Ability to comply with study requirements and complete study questionnaires
17. Adequate hematologic and end-organ function, as defined by the following laboratory results (obtained ≤ 14 days before Day 1):
 - a) Absolute neutrophil count $\geq 1.5 \times 10^9/\text{L}$
 - b) Platelet count $\geq 100 \times 10^9/\text{L}$
 - c) Hemoglobin ≥ 9 g/dL (≥ 28 days after growth factor support or transfusion)
 - d) Estimated glomerular filtration rate ≥ 30 mL/min/1.73 m² by the [Chronic Kidney Disease Epidemiology Collaboration \(CKD-EPI\)](#) equation ([Appendix 11](#))
 - e) Total serum bilirubin ≤ 1.5 x upper limit of normal (ULN)

- $\leq 4 \times$ ULN, if Gilbert's syndrome or if indirect bilirubin concentrations are suggestive of extrahepatic source of elevation
 - f) Aspartate and alanine aminotransferase $\leq 3 \times$ ULN
 - $\leq 5 \times$ ULN for a patient with liver metastases
18. Nonsterile males and female partners of nonsterile male study patients must agree to practice highly effective methods of birth control ([Appendix 4](#)) for the duration of the study and for at least 6 months after the last dose of pamiparib. Nonsterile males must avoid sperm donation for the duration of the study and for at least 6 months after the last dose of pamiparib.

4.2. Exclusion Criteria

Patients will be excluded from the study for any of the following reasons:

1. Unresolved acute adverse effects of prior therapy of \geq Grade 2
 - Except for AEs not considered a likely safety risk by investigator judgement (eg, alopecia, neuropathy, and specific laboratory abnormalities)
2. Chemotherapy, hormonal therapy, biologic therapy, radionuclide therapy, immunotherapy, investigational agent, Chinese anticancer medicine, or herbal remedies ≤ 5 half-lives if the half-life is known, ≤ 14 days if not known, before Day 1
 - Continued treatment with a bisphosphonate or denosumab is allowed, if administered at a stable dose ≥ 28 days before Day 1
3. Radiotherapy ≤ 21 days (≤ 14 days, if a single fraction of radiotherapy) before Day 1
4. Prior treatment for prostate cancer with any of the following:
 - a) PARP inhibitor
 - b) Platinum
 - c) Cyclophosphamide
 - d) Mitoxantrone
 - Prior treatment with sipuleucel-T or a checkpoint inhibitor (eg, nivolumab or pembrolizumab) is allowed.
5. Major surgical procedure, open biopsy, or significant traumatic injury ≤ 14 days before Day 1, or anticipation of need for major surgical procedure during the course of the study
 - Placement of a vascular access device is not considered major surgery.
6. Diagnosis of myelodysplastic syndrome (MDS)
7. Other diagnosis of malignancy (including, but not limited to AML)
 - Except for surgically excised nonmelanoma skin cancer, adequately treated non-invasive bladder cancer, or a malignancy diagnosed > 2 years ago with no current evidence of disease and no therapy ≤ 2 years before Day 1
8. Leptomeningeal disease or uncontrolled, untreated brain metastases

- Patients with a history of treated and, at the time of screening, asymptomatic brain metastases are eligible, provided they meet all of the following:
 - Only supratentorial metastases
 - Brain imaging at screening without evidence of interim progression
 - No ongoing requirement for corticosteroids as therapy for brain metastases
 - Anticonvulsants at a stable dose allowed
 - No stereotactic radiation or whole-brain radiation \leq 14 days before Day 1
9. Active infection requiring systemic treatment, acute/viral hepatitis or active chronic hepatitis B or C infection, or active tuberculosis
- Patients with untreated chronic hepatitis B or chronic hepatitis B virus (HBV) carriers whose HBV DNA is $>$ 500 IU/mL or patients with active hepatitis C should be excluded. Note: Inactive hepatitis B surface antigen carriers, treated and stable hepatitis B (HBV DNA $<$ 500 IU/mL), and cured hepatitis C patients can be enrolled.
10. Any of the following cardiovascular criteria:
- a) Cardiac chest pain, defined as moderate pain that limits instrumental activities of daily living, \leq 28 days before Day 1
 - b) Symptomatic pulmonary embolism \leq 28 days before Day 1
 - c) Any history of acute myocardial infarction \leq 6 months before Day 1
 - d) Any history of heart failure meeting New York Heart Association Classification III or IV ([Appendix 5](#)) \leq 6 months before Day 1
 - e) Any event of ventricular arrhythmia \geq Grade 2 in severity \leq 6 months before Day 1
 - f) Any history of cerebral vascular accident \leq 6 months before Day 1
11. Previous complete gastric resection, chronic diarrhea, active inflammatory gastrointestinal disease, or any other disease-causing malabsorption syndrome
- Gastroesophageal reflux disease under treatment with proton-pump inhibitors is allowed.
12. Active bleeding disorder, including gastrointestinal bleeding, as evidenced by hematemesis, significant hemoptysis, or melena \leq 6 months before Day 1
13. Use \leq 5 half-lives if the half-life is known, \leq 14 days if not known, before Day 1 or anticipated need for food or drugs known to be strong or moderate cytochrome P450 (CYP) 3A inhibitors or strong CYP3A inducers ([Appendix 6](#))
14. Serum creatinine $>$ 2.5 mg/dL at screening
15. Significant intercurrent illness that may result in the patient's death before death from prostate cancer
16. Known history of intolerance to the excipients of the pamiparib capsule

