5. STUDY PHASES FROM SCREENING TO END OF STUDY

5.1. Screening

As part of the Screening Visit, study center personnel will explain to the potential patient all aspects of the study, obtain signed informed consent, and document the informed consent process in the patient's source documents before any study-specific procedures are conducted. The signed ICF initiates screening that must occur within 28 days before Day 1.

Required screening assessments, some with shorter screening windows, are listed in [Appendix 1](#). Assessments obtained within 7 days of Day 1 do not have to be repeated on Day 1. Patient treatment authorization may occur as late as Day 1 before the first dose of pamiparib. Results of standard of-care tests or examinations performed before obtaining informed consent and within the screening windows may be used and do not have to be repeated as long as they meet protocol specifications.

The investigator and study center radiologist will assess the potential patient for eligibility. Repeating screening assessments within the original screening window is allowed if the patient did not previously meet certain eligibility criteria. Tumor assessments should not be repeated. Screen failures and consent withdrawals will be documented in the patients' source documents.

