5.2. Enrollment

After consent has been obtained, each patient will be assigned a unique patient number that cannot be reassigned to any other patient. Patient numbers will be assigned in chronological order starting with the lowest number. After determination of eligibility, the investigator will complete the supporting documentation and provide them to the sponsor and/or designee for review and subsequent approval. No eligibility waivers will be granted.

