7.3.1.2. Screening Tumor Assessment

The baseline tumor assessment should include the following:

- Diagnostic-quality, contrast-enhanced CT scans of chest, abdomen, and pelvis
 - To be suitable for RECIST Version 1.1 assessments, CT scans should have a maximum thickness of 5 mm and no gaps.
 - CT is the preferred imaging method for tumor assessments of chest, abdomen, and pelvis.
 - If a positron-emission tomography/CT scan is performed, the CT portion should meet the CT scan requirements described above.
 - In patients for whom the preferred CT scans are contraindicated because of, for example, a CT intravenous contrast allergy, a CT of the chest without contrast and MRI of the abdomen and pelvis with contrast are recommended.
 - MRI scans may be performed in lieu of CT scans. At screening, tumor assessments should include a diagnostic quality, contrast-enhanced MRI scan of chest, abdomen, and pelvis. To be suitable for RECIST Version 1.1 assessments, MRI scans should ideally have a maximum thickness of 5 mm and minimal gaps.
- Whole-body radionuclide bone scan to evaluate for bone metastases
- CT scan of the neck, if clinically indicated
 - Only to be performed at screening if the patient has known or suspected metastases in this area
 - MRI scan of the neck may be substituted for CT scan of the neck.
- MRI scan of the brain, if clinically indicated
 - Only to be performed at screening if the patient has symptoms that could be due to brain metastases
 - MRI is the preferred imaging method for tumor assessments of the brain.
 - In patients for whom MRI of the brain is not available or who are claustrophobic, a CT scan of the brain with intravenous contrast may be performed.

If brain metastases are present at baseline, the patient is eligible for this study if criteria listed under Exclusion Criterion 8 ([Section 4.2](#)) are met.

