APPENDIX 1. SCHEDULE OF ASSESSMENTS

Study Phase	Pre-screening ^a	Screening ^a	Treatment ^b					Un-scheduled Visit ^c	End-of-Treatment (EOT) Visit ^d	Safety Follow-up ^e	Long-term Follow-up ^f
			Cycle 1		Cycle 2		Cycle ≥3				
			Day 1	Day 15	Day 1	Day 15	Day 1				
Allowed time window	≤ 28	-28 to -1		± 2	± 3	± 3	± 5				
Study Day	≤ 28	-28 to -1	1	15	29	43	57, 85, etc.	Varies	Varies	Varies	Varies
CT with intravenous contrast of chest, abdomen and pelvis ^l		X					X (q8w ± 7d for 24 weeks, then q12w ± 7d)	X	X		X (~q12w)
Bone scan ^m		X					X (q8w ± 7d for 24 weeks, then q12w ± 7d)	X	X		X (~q12w)
MRI scan of brain, if clinically indicated ⁿ		X						X			
Patient treatment authorization		X ^a									
Pamiparib			Twice a day dosing continuously								
Pamiparib dispensing/accountability			X		X		X	X	X		
Adverse events ^o		X	X	X	X	X	X	X	X	X	X
Concomitant medication(s) ^p		X	X	X	X	X	X	X	X	X	X (~q12w)
Pharmacokinetics ^q			X	X							
Blood sample for CTCs ^r	X	X	X				X (q8w ± 7d for 24 weeks, then q12w ± 7d)		X		

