- l. Following the screening tumor assessment, tumor assessments will occur at the schedule of every 8 weeks (± 7 days) after Day 1 for the first 24 weeks, then at the schedule of every 12 weeks (± 7 days). Any measurable disease must be documented at screening and reassessed at each subsequent tumor evaluation. The same imaging method(s) used at screening must be used throughout the study. A documented standard-of-care tumor assessment may be used as the screening assessment provided it meets protocol requirements ([Section 7.3.1.2](#)). CT scan with intravenous contrast is the preferred imaging method for assessment of chest, abdomen, and pelvis. Other imaging methods are allowed as outlined in [Section 7.3.1.2](#). Imaging of other areas of disease should be performed every 8 weeks ± 7 days for 24 weeks, then every 12 weeks ± 7 days. Patients without PD at the EOT Visit should be followed with tumor

assessments every 12 weeks (± 7 days) during the long-term follow-up phase.

- m. Whole-body radionuclide bone scan must be performed at screening and will then occur at the schedule of every 8 weeks (± 7 days) after Day 1 for the first 24 weeks, then at the schedule of every 12 weeks (± 7 days). Patients without PD at the EOT Visit should be followed with bone scans every 12 weeks (± 7 days) during the long-term follow-up phase.
- n. MRI scan of the brain to assess for brain metastases must be performed at screening if the patient has symptoms that could be due to brain metastases. CT scan with intravenous contrast is acceptable if MRI is not available or the patient is claustrophobic. If brain metastases are present at baseline, the patient is eligible for this study if criteria listed under Exclusion Criterion 8 are met.
- o. AEs and laboratory safety measurements will be recorded at each study visit, graded per National Cancer Institute-Common Terminology Criteria for Adverse Events Version 4.03 or higher, and assessed as outlined in [Section 9](#). After the informed consent form has been signed, but before initiation of pamiparib, only SAEs should be reported. After initiation of pamiparib, all AEs and SAEs, regardless of relationship to pamiparib, will be reported until 30 days after last dose of pamiparib or initiation of new anticancer therapy, whichever occurs first. After this period, the investigator should report any SAEs that are believed to be related to pamiparib.

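### Section 7.3.1.2 limits the screening brain scan to patients with symptoms, which is inconsistent with the scan Exclusion Criterion 8 requires of patients with treated, asymptomatic brain metastases

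*Protocol*

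**What the plan says.** **Eligibility.** Exclusion Criterion 8 in Protocol Section 4.2 bars leptomeningeal disease and uncontrolled, untreated brain metastases, then makes an exception: "Patients with a history of treated and, at the time of screening, asymptomatic brain metastases are eligible, provided they meet all of the following". The imaging condition in the list that follows is "Brain imaging at screening without evidence of interim progression".

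**Screening procedure.** Section 7.3.1.2 lists brain MRI among the baseline assessments, when clinically indicated, and adds: "Only to be performed at screening if the patient has symptoms that could be due to brain metastases". CT with contrast may replace MRI that is unavailable or that a claustrophobic patient cannot have. The section closes by saying that a patient with brain metastases at baseline is eligible if he meets Criterion 8.

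**Schedule.** Section 5.1 points to Appendix 1: "Required screening assessments, some with shorter screening windows, are listed in". The row there reads "MRI scan of brain, if clinically indicated" and is marked at screening. Note n says the scan "must be performed at screening if the patient has symptoms that could be due to brain metastases", and repeats the reference to Criterion 8.

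**Safeguards.** Section 5.1 accepts existing standard-of-care results: "tests or examinations performed before obtaining informed consent and within the screening windows may be used". Under Section 5.2 the investigator must complete the eligibility documents and "provide them to the sponsor and/or designee for review and subsequent approval", and no eligibility waivers are given.

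**The concern.** The exception in Criterion 8 is defined by the absence of symptoms and makes a screening brain scan a condition of entry. The procedural section makes the presence of symptoms the sole reason to do that scan. One section asks for the scan and another, read literally, withholds it from the same patient.

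Two errors could follow. A site may enroll the patient unscanned, so that progression in the brain since treatment goes unchecked unless sponsor review catches the gap. Or a site may conclude that the imaging condition cannot be met and screen-fail a patient whom the protocol means to admit. With about 45 centers planned, different sites could read the text differently.

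**Working it through.** The plan states no figure on this point, so the check is a comparison of texts, followed by a rough size under a stated assumption.

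**Step 1. Apply each rule to each kind of patient.**

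| Patient at screening | Criterion 8 | Section 7.3.1.2 | Appendix 1 note n |
|---|---|---|---|
| No known brain metastases, no symptoms | silent | no scan | silent |
| Symptoms that suggest brain metastases | excluded if metastases are found uncontrolled and untreated | scan | scan required |
| Treated brain metastases, no symptoms | scan required, with no interim progression | no scan, because of *only* | silent |

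The rules disagree in the third row alone. Note n does not share the fault: it sets a minimum for patients with symptoms and bars nothing. It does not call for the scan in the third row either.

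**Step 2. Look for text that settles the third row.**

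- The closing sentence of 7.3.1.2, and its repeat in note n, send a patient with baseline brain metastases to Criterion 8. That points the site to the right rule but leaves the restriction in place.
- The clinically-indicated wording in 7.3.1.2 and in the Appendix 1 row permits the scan. In 7.3.1.2, though, the sub-bullet beneath it narrows the indication to symptoms.
- The contrast CT option sits under the same bullet. It changes the modality and leaves the trigger as it is.
- Section 7.3.1.3 calls for imaging of other known disease sites, but on study, not at screening.
- The neck CT bullet in the same list is triggered by metastases known or suspected in that area. The brain bullet has no such limb, which suggests an oversight.

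**Step 3. Rough size.** The documents give no count or prevalence. *Assumption:* a fraction p of 0.5%, 1% or 2% of patients has treated, asymptomatic brain metastases. The planned n is approximately 100 (Protocol Section 10.6). SAP Section 8 reports 13 enrolled at termination. The expected number is n × p, and the chance of at least one is 1 − (1 − p)^n.

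| p | Expected, n = 100 | At least one, n = 100 | Expected, n = 13 | At least one, n = 13 |
|---|---|---|---|---|
| 0.5% | 0.5 | 1 − 0.995^100 = 39.4% | 0.065 | 1 − 0.995^13 = 6.3% |
| 1% | 1.0 | 1 − 0.99^100 = 63.4% | 0.13 | 1 − 0.99^13 = 12.2% |
| 2% | 2.0 | 1 − 0.98^100 = 86.7% | 0.26 | 1 − 0.98^13 = 23.1% |

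These are chances that such a patient is present. They are not chances that a scan is missed or that a patient is wrongly refused.

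**The case against.** The strongest reply is that a competent site would not go wrong. Criterion 8 is explicit, and the section containing the restriction itself refers back to it. Appendix 1, the list of required assessments, marks the scan at screening when clinically indicated and has no *only*. Appendix 2 asks for all sites of disease to be recorded at baseline, and Appendix 10 lists the central nervous system among sites to record. Enrolling an unscanned patient would take both a site that overlooks an eligibility condition and a sponsor review that misses it.

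Most of this stands, and it is why the point is minor. It lowers the chance of error without curing the text, because none of these places lifts the restriction or names the group.

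A reader might infer that the two rules can never both be met. The documents do not support that. Criterion 8 asks for brain imaging at screening without saying that the study must order it, and Section 5.1 accepts an in-window standard-of-care scan. Such a patient satisfies both sections.

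A reader might also infer damage to the response or progression endpoints, since Appendix 2 treats a lesion found later at a site not scanned at baseline as new, hence as progression. That would need a skipped baseline scan, a later brain scan, and a known treated lesion then read as new. Nothing in the documents shows that chain occurring or gives it a frequency.

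**Conclusion.** The inconsistency is in the current protocol text and should be corrected. It concerns one sub-bullet in Section 7.3.1.2, with a matching gap in Appendix 1 note n. It bears on an eligibility safety check in a group that is probably small and whose size the documents do not give. The finding itself rests on wording alone. Only the size estimate depends on the assumed 0.5% to 2%.

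No endpoint analysis, sample size, power or alpha figure changes. The trial stopped after 13 patients, and the documents do not say whether any of them had brain metastases, so nothing here shows that a patient was affected. The point is about the protocol as written for about 100.

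**What to change.** In the brain MRI sub-bullet of Section 7.3.1.2, delete *only* and give two triggers: the existing symptom trigger, or a history of brain metastases. Put the same two triggers in Appendix 1 note n. Keep contrast CT as the alternative where MRI is unavailable or the patient is claustrophobic.

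The cost is wording in two places. No procedure is added: patients with treated, asymptomatic metastases already need the scan under Criterion 8, those with symptoms are already covered, and those with uncontrolled, untreated metastases are excluded. The on-study imaging schedule is unchanged. Section 11.3.1 requires protocol modifications to be submitted to authorities and ethics committees, so the change would best travel with another amendment.
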